### 13.7.3 Skin Toxicity Monitoring among Patients Treated with 18 mg/kg Sym004

Interim analyses that focus on the physiologic consequences of Sym004 treatment will be conducted after 19 total patients across both cohorts have been treated with Sym004. The goal of the interim analysis is to determine whether the dose of Sym004 needs to be increased or decreased. The basis of this decision will partly be based upon the prevalence of  $\geq$  Grade 3 skin toxicity after the administration of 2 doses. However, other factors may contribute to this decision-making. Accrual will be not be suspended while this assessment of skin toxicity is occurring. The decision-making could result in 3 outcomes: increase the dose, decrease the dose, or continue accruing at the current dose. If a decision is made to modify the dose, the protocol will be appropriately amended.

If the prevalence of skin toxicity is truly 30% (Symphogen unpublished data), then the dose of Sym004 is considered acceptable. However, if the true prevalence of skin toxicity is much less or much greater than 30%, then the dose of Sym004 may need modification. Observing skin toxicity in 2 or fewer patients or 9 or more patients is an indication that the data concerning dosing needs to be carefully scrutinized along with other available data. The probability of observing this extent of skin toxicity as a function of the true probability of skin toxicity is tabulated below.

True Probability of Skin Toxicity	Probability of observing either 2 or fewer patients with skin toxicity, or observing 9 or more patients with skin toxicity
0.05	0.933
0.1	0.705
0.3	0.130
0.5	0.677
0.55	0.816
0.6	0.912
0.65	0.965

### 13.7.4 Initial Toxicity Monitoring among Patients Treated with 24 mg/kg Sym004

Given limited experience with 24 mg/kg Sym004, the first 3-6 patients will be slowly accrued and carefully monitored for unacceptable toxicity (see Section 7.1.2).

The first patient, regardless of cohort, will be treated and observed for 1 cycle before the accrual of a second patient. During this period of observation, the patient will receive at minimum 2 full doses of Sym004 and be followed until the end of Cycle 1. If the patient experiences an unacceptable adverse event (refer to Section 7.1.2), the study will be suspended and the patient's experience will be discussed with Symphogen to determine whether patient accrual should continue. Otherwise, 2 additional patients will be treated.

The second and third patient can be accrued at the same time. However, further accrual after the 3rd patient is suspended until completion of 1 cycle of therapy. After the first 3 patients have been observed, the number of patients with unacceptable toxicity will be determined.

- If none of the first 3 patients has an unacceptable toxic event, accrual will continue without further slowed accrual.
- If 2 of the first 3 patients has an unacceptable toxicity, the study will remain suspended. Results will be discussed with Symphogen with the expectation that accrual will be terminated.
- If 1 of the first 3 patients has an unacceptable toxicity, an additional 3 patients can be accrued after which accrual will be suspended until all patients have been observed for at least 1 cycle. If none of the additional 3 patients experiences an unacceptable toxicity, then accrual will resume without the requirement of staggered entry. If 1 of these 3 patients experiences an unacceptable toxicity, the study will remain suspended while a discussion occurs with Symphogen to determine if accrual is terminated.

For initial monitoring of the 24 mg/kg dose of Sym004, an unacceptable adverse event is defined as any grade 3, 4, or 5 adverse event that is definitely, possibly, or potentially related to Sym004 treatment.

Patients who have their dose escalated from 18 mg/kg to 24 mg/kg will be considered as part of this interim analyses of toxicity at the 24 mg/kg if they are among the first 3 (or 6) patients who receive Sym004 at the 24 mg/kg dose level.

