### 11.2.1 Reporting of SAEs to Duke Cancer Institute Safety Desk

Adverse events that are serious and unexpected are considered reportable. Reportable events that occur during the study, beginning at the time of first study drug treatment infusion) to within 30 days following cessation of study drug treatment are reportable.

The study team will complete the DCI SAE Report Form and the DCI Safety Review Form, which will both be submitted to the DCI Safety Desk ([contact] or secure email to [[contact]](mailto:[contact])) and to the PI, [name], MD, FRCPC (email: [[contact]](mailto:[contact])) or her designee within 24 hours of knowledge of the event.

The initial report for each SAE should include at minimum the following information:

- protocol # and title
- patient initials, study identification number, sex, age or date of birth
- date the event occurred
- description of the SAE
- dose level and cycle number at the time the SAE occurred
- description of the patient's condition
- indication whether the patient remains on study
- causality or causal relationship

The DCI Safety Desk will track individual SAE reports into their internal tracking database and complete the initial processing within 2 business days of receipt. For unanticipated study-related event(s), these will be processed within 1 business day of receipt.

De-identified source documentation (i.e. admission notes, discharge notes, applicable laboratory results, radiology/diagnostic testing results, etc.) should be sent with the SAE Report Form, if available at the time of the report. Any follow-up information including severity, action taken, concomitant medications, and outcome should be communicated to the DCI Safety Desk, as soon as possible using the same forms mentioned above. The study team should keep a copy of the initial SAE forms submitted to the DCI safety desk and any SAE follow up forms for reference.

The DCI Safety Desk will use the information provided in the DCI SAE Report Form and the DCI Safety Review Form to complete a FDA Form 3500A, and will submit it to the Duke University IRB, if it meets Duke IRB reporting requirements (see below).

Only adverse events that the Duke Sponsor-Investigator determines to be serious, unanticipated, and related or possibly/probably (i.e. more likely than not) related to the research must be reported to the Duke IRB. Those adverse events will be submitted in the electronic IRB (eIRB) system, according the following guidelines:

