- Report within 24 hours of learning about any subject's death that was unanticipated and more likely related to the research than unrelated;
- Report within 5 business days of learning about any serious, unanticipated, and related or possibly/probably related adverse event;
- Report within 10 business day of learning about any other unanticipated problem or event that was more likely related to the research than unrelated.
- The Sponsor-Investigator must report to the FDA, in an IND safety report, any suspected adverse reaction that is both serious and unexpected. Before submitting this report, the sponsor needs to ensure that the event meets all three of the definitions contained in the requirement:
  - Suspected adverse reaction (i.e. there is a reasonable possibility that the drug caused the adverse event)
  - Serious
  - Unexpected

If the adverse event does not meet all three of the definitions, it should not be submitted as an expedited IND safety report.

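### At 24 mg/kg, a related death as the only event in patient 2 or 3 lets three more patients enrol without the discussion with Symphogen that the same event requires in patient 1

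*Combined protocol and SAP*

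**What the plan says.** Section 13.7.4 governs the run-in at 24 mg/kg. Its trigger is broad: "an unacceptable adverse event is defined as any grade 3, 4, or 5 adverse event that is definitely, possibly, or potentially related" to Sym004.

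Patient 1 is treated alone and observed for one cycle. If that patient has an unacceptable event, the study is suspended and the case "will be discussed with Symphogen to determine whether patient accrual should continue". Otherwise two more patients are treated, and staggering between them is not required: "The second and third patient can be accrued at the same time". Accrual is then held until one cycle is complete, after which "the number of patients with unacceptable toxicity will be determined".

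That count selects the next step:

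- No patient affected: accrual continues at the normal pace.
- Two of three affected: the suspension stays and results go to Symphogen, with termination expected.
- One of three affected: "If 1 of the first 3 patients has an unacceptable toxicity, an additional 3 patients can be accrued".

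For the additional three, no event releases accrual from staggered entry. One event keeps the suspension in place: "If 1 of these 3 patients experiences an unacceptable toxicity, the study will remain suspended while a discussion occurs with Symphogen".

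Section 13.7.4 refers to Section 7.1.2, which is a dose-reduction rule for grade 3-4 toxicity and says nothing about grade 5.

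**The concern.** The rule counts affected patients and ignores grade, so a related death weighs the same as a related grade 3 rash. Its required discussion also depends on who has the event. A grade 3 event in patient 1 stops the study until Symphogen has been consulted. A related death in patient 2 or 3, with no other event, does not. Followed exactly, the rule then allows three more exposures and, if those patients are event-free, unrestricted accrual.

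Section 13.7.4 itself gives limited experience at this dose as the reason for the run-in, and the other Sym004 studies described in Sections 7.1.3 and 7.2 went no higher than 18 mg/kg every other week. It is also the only prespecified toxicity rule on accrual at 24 mg/kg: Section 13.7.2 concerns efficacy and Section 13.7.3 concerns 18 mg/kg. Once the run-in releases accrual, up to 65 patients may be treated at this dose (Section 13).

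**Working it through.** **Step 1: trace a related death through each branch.** The plan states no operating characteristic for this rule, so there is no figure to reproduce.

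| Related death occurs in | Other events | What 13.7.4 requires | Discussion with Symphogen required? |
|---|---|---|---|
| Patient 1 | none | suspend the study | yes |
| Patient 2 or 3 | none in the first 3 | 3 more patients may enter after the one-cycle hold | **no** |
| Patient 2 or 3 | one other of the first 3 affected | remain suspended | yes |
| One of the additional 3 | one earlier event in the first 3 | remain suspended | yes |

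The last row is a second event overall, so the like-for-like comparison is row 1 against row 2. The hold starts only after patient 3. If patient 2 dies before patient 3 is enrolled, nothing in 13.7.4 bars that enrolment either.

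**Step 2: look for a safeguard elsewhere.**

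- Section 11.2.1 sends serious, unexpected events to the Safety Desk and the PI "within 24 hours of knowledge of the event". The 24-hour IRB report covers a "death that was unanticipated and more likely related to the research than unrelated". This is narrower than 13.7.4, which also counts possibly related events.
- Section 11.2.2 requires FDA reports of unexpected, suspected fatal reactions within 7 days.
- Section 11.2.3 requires notice of any on-study death to Symphogen within 2 business days, and of urgent safety issues within 24 hours.
- Section 7.4 (termination by the PI-sponsor) and Section 12.1 (additional monitoring) are discretionary.
- Section 11.6 provides annual committee review. Section 11.7 states that an external DSMB is not applicable.

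These are duties to report or powers to act. None makes a decision on accrual a condition of enrolling patient 4.

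**Step 3: how often could it happen?** Let q be the per-patient probability of a related grade 5 event in cycle 1, r that of any other unacceptable event, and s = 1 − q − r. Patients are treated as independent and exchangeable.

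- q is not in the documents. Assumed: 0.5%, 2%, 5%.
- r = 10.5% is grade 3 skin toxicity at 18 mg/kg in this trial (2/19, Section 7.2).
- r = 20% is an assumed middle value.
- r = 41.2% is grade 3 skin toxicity at 18 mg/kg every other week in subjects previously given anti-EGFR antibodies (Section 7.1.3). Exclusion 2 bars such patients, so this is only a high sensitivity value.

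P(death in patient 2 or 3 is the only event in the first 3) = 2qs². P(next 3 event-free) = s³. P(both, so accrual is fully released) = 2qs⁵.

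Example with q = 2% and r = 10.5%: s = 0.875. Then 2 × 0.02 × 0.875² = 0.0306; 0.875³ = 0.670; product 0.0205.

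| q | r | Enters the branch, 2qs² | Then fully released, 2qs⁵ |
|---|---|---|---|
| 0.5% | 10.5% | 0.8% | 0.6% |
| 0.5% | 20% | 0.6% | 0.3% |
| 0.5% | 41.2% | 0.3% | 0.07% |
| 2% | 10.5% | 3.1% | 2.1% |
| 2% | 20% | 2.4% | 1.2% |
| 2% | 41.2% | 1.3% | 0.2% |
| 5% | 10.5% | 7.1% | 4.3% |
| 5% | 20% | 5.6% | 2.4% |
| 5% | 41.2% | 2.9% | 0.5% |

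Skin toxicity alone understates r. Grade 3-4 hypomagnesemia (0-38%, Section 7.1.3) also counts when related. A higher r makes the branch rarer.

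**The case against.** The strongest reply is that the practical gap is small. The one-cycle hold after patient 3 means that a cycle 1 death in patient 2 or 3 would normally occur before patient 4 could enter. By then Symphogen should have been notified, and the IRB and FDA too if their criteria were met. The wording is permissive: three more patients may be accrued, not must be. The sponsor-investigator can stop at any time, and most would pause.

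Patient 1 is also a sentinel, treated alone, and one event in one patient is a different signal from one in three. Expanding by three after one event is a coherent count-based design, and the asymmetry covers any grade 3-5 event, so death is simply its worst case. A counted death need only be possibly related, which Section 11.1 defines as one that may be related. Finally, q has no documentary basis. The 7% corner pairs the highest q with the lowest r, although Section 7.2 expects more skin toxicity at 24 mg/kg. The model also ignores that patients escalated from 18 mg/kg may be among the first 3, having been selected for tolerating the lower dose.

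Much of this stands. The hold and the notifications narrow the gap, and the probabilities show sensitivity only. But notification is not a decision, and discretion is what a written run-in rule is meant to replace. The sentinel argument explains why one grade 3 event in patient 1 gets special handling. It does not explain why a related death in patient 2 or 3 should need less than that.

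**Conclusion.** The concern holds. Section 13.7.4 gives a related death the same weight as a related grade 3 event, and the branch for a sole event in patient 2 or 3 omits the discussion required for patient 1. Grading, attribution and reporting would still take place; what is missing is a required discussion and accrual decision before the next enrolment. This conclusion comes from the text and needs no assumed rate.

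The frequency does need assumptions: roughly 0.3% to 7% for entering the branch, and 0.07% to 4.3% for entering it and then reaching full release, over the ranges above. The branch is rare. The point should be addressed because of what the rule permits after a related death, not because that is likely.

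**What to change.** Add one sentence to Section 13.7.4, ahead of the count-based branches:

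> Any grade 5 event counted as related to Sym004 in any of the first 3 to 6 patients treated at 24 mg/kg immediately suspends accrual until the case has been reviewed and discussed with Symphogen and a decision on continuing has been made; this applies before any count of affected patients.

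Keep the present counts for grades 3 and 4. The sentence extends the patient 1 step to patients 2 and 3, and makes the trigger immediate, so a death in patient 2 would also hold patient 3 if not yet enrolled. For the additional three it changes only the timing: one event there already leads to a discussion, but only after all three have been accrued and observed.

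No extra patients, staff or study procedures are needed. The cost is a protocol amendment with IRB approval (Section 14.7), one case review if the event occurs, and a short accrual pause that for patients 2 and 3 would largely overlap the existing hold. Under the revised rule, the probability of passing from a sole related death in patient 2 or 3 to further enrolment without discussion becomes zero.

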### **3.4 Data Analysis and Statistical Considerations**

Kaplan-Meier curves will be generated to describe the PFS and OS experience of patients enrolled on this protocol within each cohort and dose level. Progression-free survival (PFS) is defined as the time interval between initiation of protocol treatment and either disease progression or death. If the patient is alive and progression-free, PFS will be censored at the date last known alive. Overall survival (OS) is defined as the time interval between initiation of protocol treatment and death, or date of last follow-up if alive. Estimates with confidence intervals will be generated for median PFS and OS, as well as 2 month intervals for PFS for the first year (2, 4, 6, etc..) and 6 month intervals for OS for the first 2 years (6, 12, 18, 24) from the time the subject goes on study.

Radiographic response rate will be estimated as the proportion of treated patients with a complete or partial response (see Appendix B). An exact binomial confidence interval will be generated.

[figure not shown]
For each type of toxicity, the maximum grade experienced by each patient will be summarized with frequency distributions within each cohort and dose level. Two adverse experience tabulations will be generated, one that includes all toxicities regardless of attribution, and one that includes only toxicities that are possibly, probably, and definitely related to Sym004 treatment.

Cox proportional hazards model will be used to examine the association between EGFRvIII expression and PFS and OS.

At the 18 mg/kg dose level, interim analyses will be conducted after 19 total patients across both cohorts have been treated with Sym004. These interim analyses will focus on the prevalence of skin toxicities.

With each cohort of the study at the 24 mg/kg dose level, the study is designed as a two-stage study to assess 6-month PFS. After the initial stage, interim futility analyses will be conducted.

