## **10.4 Re-treatment Criteria (day 1 and day 15)**

Subjects must meet the following re-treatment criteria prior to infusion with Sym004, in order to receive the next scheduled infusion. Dose modifications are allowed as described in Section 7.1.1.

- ANC  $\geq$  1,000 cells/ $\mu$ l
- Platelets  $\geq$  50,000 cells/ $\mu$ l
- AST, bilirubin, creatinine  $\leq$  2.0 x upper limit of normal
- Resolution of any grade 3 or greater toxicity felt to be possibly, probably or definitely attributable to the study regimen to grade 2 or lower based on the investigator's decision.

If treatment with Sym004 is delayed for longer than 2 weeks due to toxicities (i.e. grade 3-4 non-hematologic toxicities secondary to Sym004, such as skin toxicities, electrolyte disturbances, and gastrointestinal symptoms, or grade 4 neutropenia or thrombocytopenia), the MRI assessment that would normally occur prior to beginning a new cycle or at the end of treatment will still be obtained no later than  $8 \pm 2$  weeks after the previous MRI assessment. Once the toxicities have resolved to meet re-treatment criteria, the subject will resume Sym004. The day Sym004 is resumed will be considered Day 1 of the next cycle expected for the subject, which means that we will omit day 15 infusion for the previous cycle.

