### 11.1 Adverse Events

An adverse event (AE) is any untoward medical occurrence in a subject receiving study drug and which does not necessarily have a causal relationship with this treatment. For this protocol, the definition of AE also includes worsening of any pre-existing medical condition. An AE can therefore be any unfavorable and unintended or worsening sign (including an abnormal laboratory finding), symptom, or disease temporally associated with the use of Sym004, whether or not related to use of the Sym004. Abnormal laboratory findings without clinical significance (based on the PI's judgment) should not be recorded as AEs. But laboratory value changes that require therapy or adjustment in prior therapy are considered adverse events.

From the time the subject signs the informed consent form through the End of Study visit (as defined in Section 10.5), all AEs must be recorded in the subject medical record and adverse events case report form.

AEs will be assessed according to the CTCAE version 4.0. If CTCAE grading does not exist for an AE, the severity of the AE will be graded as mild (1), moderate (2), severe (3), life-threatening (4), or fatal (5).

Attribution of AEs will be indicated as follows:

- Definite: The AE is clearly related to the study drug
- Probably: The AE is likely related to the study drug
- Possible: The AE may be related to the study drug
- Unlikely: The AE is doubtfully related to the study drug
- Unrelated: The AE is clearly NOT related to the study drug

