### 13.5.1 Key Secondary Objective: Safety

Within each cohort and dose level, the proportion of patients who experience grade 3, 4, or 5 adverse events that are possibly, probably, and definitely related to protocol treatment will be estimated.

In addition, for each type of toxicity, the maximum grade experienced by each patient will be summarized with frequency distributions. Two adverse experience tabulations will be generated, one that includes all toxicities regardless of attribution, and one that includes only toxicities that are possible, probably, and definitely related to Sym004 treatment.

Patients who have their dose escalated from 18 mg/kg to 24 mg/kg will be included in toxicity summaries for 18 mg/kg and 24 mg/kg. The toxicity experienced prior to dose escalation will be summarized with the other patients treated at the 18 mg/kg dose level; whereas, the toxicity experienced after dose escalation will be included in the summary of adverse events associated with 24 mg/kg.

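### The event definition for the first 3 to 6 patients at 24 mg/kg does not match the recorded attribution codes, so which events trigger the check is ambiguous

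*Combined protocol and SAP*

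**What the plan says.** Section 13.7.4 staggers entry at 24 mg/kg because experience at that dose is limited. An unacceptable event in patient 1 suspends the study for discussion with the drug's manufacturer. After three patients, a count of 0 lets accrual continue, a count of 1 adds three more patients, and a count of 2 keeps the study suspended. After a count of 1, accrual resumes only if none of the additional three patients has an event.

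The section closes by defining the counted event as "any grade 3, 4, or 5 adverse event that is definitely, possibly, or potentially related to Sym004 treatment". Earlier in the same section, the reader is referred twice to section 7.1.2 for what is unacceptable.

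Section 11.1 sets the attribution scale on which every adverse event is recorded. Its top three levels are "Definite: The AE is clearly related to the study drug", "Probably: The AE is likely related to the study drug" and "Possible: The AE may be related to the study drug". The other two are Unlikely and Unrelated.

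Three other sections list the levels that count as related:

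- The synopsis (section 3.4) tabulates "only toxicities that are possibly, probably, and definitely related to Sym004 treatment".
- The re-treatment criteria (section 10.4) refer to toxicity "felt to be possibly, probably or definitely attributable to the study regimen".
- The key secondary safety endpoint (section 13.5.1) is the proportion of patients with "grade 3, 4, or 5 adverse events that are possibly, probably, and definitely related to protocol treatment".

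**The concern.** A stopping rule based on counts has to be applied to coded records. The attribution field can hold five values, and the rule in section 13.7.4 names three terms, of which only two correspond to those values. *Potentially* has no code, and the code *Probably* has no term. Someone applying the rule must decide what the third term means, and the protocol gives no instruction.

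The ambiguity matters because of where it sits. This is the only count-based toxicity rule at 24 mg/kg. The two-stage rules in section 13.7.2 concern efficacy only, section 11.7 marks an external monitoring board as not applicable, and the committee review in section 11.6 is annual. With three patients, one classification can move the trial from one branch to another. The check could also report no qualifying event for a patient who has one under the key secondary safety endpoint.

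**Working it through.** **Step 1. Match terms to codes.** For a grade 3, 4 or 5 event:

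| Code recorded (11.1) | Related in 3.4, 10.4, 13.5.1 | 13.7.4, literal match | 13.7.4, *potentially* read broadly |
|---|---|---|---|
| Definite | yes | counted | counted |
| Probably | yes | no matching term | counted |
| Possible | yes | counted | counted |
| Unlikely | no | not counted | arguably counted |
| Unrelated | no | not counted | not counted |

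The literal reading is out of order, since a weaker attribution counts and a stronger one does not. The broad reading restores the order but may extend to events that the related-only analyses exclude. The two readings err in opposite directions.

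**Step 2. What one event does.** Suppose exactly one of the first three patients has a grade 3 event coded Probably, and no other qualifying event occurs. The literal count is 0 of 3, and accrual continues without further slowing. If Probably is counted, the result is 1 of 3, and three more patients are entered under a renewed hold. If that patient is the first one treated, the same choice decides whether the study is suspended at once.

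**Step 3. Illustration of size.** Section 13.7.4 states no operating characteristic, so there is no plan figure to reproduce. Let p be the chance that a patient has a counted event, and q = 1 − p. The chance that accrual eventually proceeds, by 0 of 3 or by 1 of 3 followed by 0 of 3, is

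A = q³ + 3pq⁵.

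The second term includes the renewed hold after the first three and the next three patients. If an event in patient 1 is treated as not proceeding, the chance is

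B = q³ + 2pq⁵.

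At p = 0.30: q³ = 0.343 and q⁵ = 0.168, so A = 0.343 + 0.9 × 0.168 = 0.494 and B = 0.343 + 0.6 × 0.168 = 0.444.

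If a share s of patients with a related event drops out of the count, p becomes p(1 − s). The documents do not give s, so a range of 25% to 50% is assumed. The reference rates are 30% (the acceptable skin toxicity prevalence in section 13.7.3) and 41.2% (grade 3 skin toxicity at 18 mg/kg every other week in section 7.1.3, in patients with earlier anti-EGFR antibody therapy). Neither is an estimate of the event rate for this check.

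| True rate | Formula | All three codes counted | s = 25% | s = 33% | s = 50% |
|---|---|---|---|---|---|
| 30% | A | 0.494 | 0.654 | 0.709 | 0.814 |
| 30% | B | 0.444 | 0.591 | 0.643 | 0.747 |
| 41.2% | A | 0.290 | 0.476 | 0.547 | 0.696 |
| 41.2% | B | 0.261 | 0.427 | 0.492 | 0.631 |

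The opposite direction is just as easy to produce. If the broad reading added events coded Unlikely and raised the counted rate from 0.30 to 0.375 (a quarter more, also assumed), A would fall from 0.494 to 0.351 and B from 0.444 to 0.316.

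The figures under the literal reading are upper-end illustrations for another reason. They treat each affected patient as having one qualifying event. A patient with a Probably event and a second grade 3 to 5 event coded Possible or Definite is still counted, so the effective s is smaller.

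**The case against.** The strongest objection is that this is an obvious slip, with *potentially* written for *probably*, and that no investigator would leave out a likely related event while counting one that may be related. In ordinary English, a likely related event is also potentially related. The protocol is loose with these words elsewhere: section 11.2.2 describes reportable serious events as possibly or probably related without naming definite, and nobody would read that as exempting definite ones. This stands. A reader might infer that probably related events are certainly left out of the check. The documents do not support that, because the wording permits the exclusion without requiring it.

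A second objection is that section 13.7.4 also points to section 7.1.2, which speaks of toxicity secondary to Sym004 and names no attribution codes, so a Probably event could qualify by that route. This is true as far as it goes, but it does not resolve the wording. Section 7.1.2 covers grade 3 to 4 non-hematologic events and grade 4 neutropenia or thrombocytopenia, with listed exceptions. Section 13.7.4 covers any grade 3 to 5 related event without exceptions. The cross-reference therefore supplies a second, conflicting definition.

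A third objection is that safeguards exist. Serious unexpected events reach the investigator and the safety desk within 24 hours, and an adverse count leads to discussion with the manufacturer, not to automatic closure. These soften the consequence, but they do not say which codes the count uses.

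**Conclusion.** The point holds as an ambiguity in the operative definition of a count-based accrual rule. Two facts can be checked directly: *potentially* is not an attribution code, and *Probably* is missing from the list, unlike in the three other sections that list related events. Depending on the reading, the check could under-count or over-count.

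The size is not known. At the level of the decision, one event classified differently can change the branch. As a probability, the shift depends wholly on the share of events coded Probably (or Unlikely), which the documents do not give. The tabulated values also assume independent patients and one qualifying event per patient. They show that the ambiguity is capable of mattering, and they do not measure the rule's actual performance.

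A reader might also infer that using the wording of section 13.5.1 would make the check and the key secondary endpoint count identical events. It would not. The check covers the first 3 to 6 patients over about one cycle, pooled across cohorts. The endpoint covers all treated patients, by cohort and dose level, without that window. Only the attribution criterion would agree.

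**What to change.** Reconcile section 13.7.4 with sections 11.1 and 13.5.1 so that the unacceptable event is defined only in recorded attribution codes, consistent with the related-event wording elsewhere in the protocol (possibly, probably, definitely). If *potentially* was meant to reach further, the codes it covers should be named.

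In the same edit, reconcile the definition with the cross-references to section 7.1.2, so that one event definition governs the check. The two sections differ in grades, exceptions and attribution wording. Which of those should apply is for the investigators to decide, and no choice is proposed here.

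The attribution change is one phrase. The reconciliation with section 7.1.2 is a further edit to the text. Neither needs additional data or patients. The downside is that the check may trigger more often than under the literal wording, which would slow early accrual at 24 mg/kg.
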